# 7.7 Early Withdrawal of Subjects

- 1. Subjects should be withdrawn from the study if they no longer wish to participate, are being uncooperative, or if the investigator feels that it is in the best interest of the subject to withdraw.
- 2. Subjects with protocol deviations or for whom it is discovered should have been excluded should not be withdrawn unless there is a safety concern. The protocol deviation should be recorded in the subject's chart and Protocol Deviation Form and included in the study report.
- 3. Subjects who experience an AE resulting in or requiring discontinuation of study product use should be encouraged to be followed in the study until the AE is resolved or stabilized.
- 4. Subjects whose treatment randomization is unblinded at the study site should be withdrawn.

- 5. If a female subject becomes pregnant during the study, study product will be discontinued immediately and she will be followed through the pregnancy and delivery. Details of the pregnancy, delivery and health of the infant should be recorded on the Pregnancy Report Form and the sponsor notified immediately.
- 6. At the time of study discontinuation, the investigator will record the reason for early withdrawal, date of last study product application, date of last visit or contact, collect AE data, and, if possible, perform all Week 12 visit-specific evaluations. Every attempt should be made to contact subjects who are lost-to-follow-up for a final safety assessment. At least three attempts must be documented in the subject's chart including the use of at least 1 certified letter. Any contact, either direct or indirect, should be made with the purpose to document the final status of the subject with regard to safety.
- 7. Subjects who withdraw early will not be replaced.

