### 11.2.3 Per-Protocol

The PP population will include all subjects in the ITT population who complete the Week 12 evaluation without any major protocol violations (i.e., any subject or investigator activity that could have possibly interfered with the therapeutic administration of the treatment or the precise evaluation of treatment efficacy).

Specifically, the PP population will include subjects in the ITT population who meet all of the following criteria:

- 1. Subject met all inclusion/exclusion criteria.
- 2. Subject did not take any prohibited concomitant medications during the evaluation period. The concomitant medication usage will be reviewed during the population determination review, remaining blinded to treatment designation, to determine

prohibited medication usage that warrants exclusion from the PP population if they met the entrance criteria without any protocol violations. This review will take into consideration the timing, duration of treatment with the concomitant medication, and influence on the efficacy and safety assessments prior to deeming a prohibited concomitant medication as a protocol violation that warrants exclusion from PP.

- 3. Completed the Week 12 visit within the allowed window.
- 4. Subject was compliant with the dosing regimen. A subject will be considered compliant if the subject applied at least 80% but no more than 120% of the expected applications during the entire evaluation period.

Subjects who prematurely discontinue from the study due to documented lack of efficacy, worsening condition, or a treatment-related AE will be included in the PP population.

Other additional criteria may be added to the list to accommodate for unforeseen events that occurred during the conduct of the trial that result in noteworthy study protocol violations. These criteria will be documented with appropriate signature at the time subject populations are finalized, prior to database lock.

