6.5.4. Per-Protocol (PP) Population

The PP population will include all subjects in the ITT population who completed the Week 12 evaluation without any major protocol violations (i.e., any subject or investigator activity that could have possibly interfered with the therapeutic administration of the treatment or the precise evaluation of treatment efficacy).

Specifically, the PP population will include subjects in the ITT population who meet all of the following criteria:

- 1. Subject met all inclusion/exclusion criteria.
- 2. Subject did not take any prohibited concomitant medications during the evaluation period. The concomitant medication usage will be reviewed during the population determination review, remaining blinded to treatment designation, to determine prohibited medication usage that warrants exclusion from the PP population if they met the entrance criteria without any protocol violations. This review will take into consideration the timing, duration of treatment with the concomitant medication, and influence on the efficacy and safety assessments prior to deeming a prohibited concomitant medication as a protocol violation that warrants exclusion from PP.
- 3. Completed the Week 12 visit within the allowed window.
- 4. Subject was compliant with the dosing regimen. A subject will be considered compliant if the subject applied at least 80% but no more than 120% of the expected applications (168 applications expected) during the entire evaluation period.

Subjects who prematurely discontinued from the study due to documented lack of efficacy, worsening condition, or a treatment-related AE will be included in the PP population.

Other additional criteria may be added to the list to accommodate for unforeseen events that occurred during the conduct of the trial that result in noteworthy study protocol violations. These criteria will be documented with appropriate signature at the time subject populations are finalized, prior to database lock.

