8.3. Analysis of the Efficacy Endpoints

The following efficacy endpoints will be summarized using descriptive statistics for both the ITT and PP populations:

- Proportion of Subjects with IGA Success at Weeks 4, 8 and 12. IGA success is defined as an IGA score of 0 (Clear) or 1 (Almost Clear) with at least a 2-grade reduction from baseline.
- Absolute Change from Baseline in Inflammatory Lesion Counts at Weeks 4, 8 and 12. The following location of lesions will be summarized separately: face and chest/back/shoulders.
- Absolute Change from Baseline in Non-Inflammatory Lesion Counts at Weeks 4, 8 and 12. The following location of lesions will be summarized separately: face and chest/back/shoulders.
- Percent Change from Baseline in Inflammatory Lesion Counts at Weeks 4, 8 and 12. The following location of lesions will be summarized separately: face and chest/back/shoulders.
- Percent Change from Baseline in Non-Inflammatory Lesion Counts at Weeks 4, 8 and 12. The following location of lesions will be summarized separately: face and chest/back/shoulders.
- Change from Baseline to Weeks 4, 8 and 12 in CADI.

For all efficacy endpoints for the ITT and PP populations, data will be summarized at week 4, 8 and 12 with data as is where missing data is not imputed.

Also for missing IGA and lesion counts in the ITT population, data will be summarized at week 12 where the primary handling method for missing data, except for baseline, will be the multiple imputation (MI) approach via regression. In details, the MI regression model will include the following predictors in the model: treatment, age, gender, baseline inflammatory lesion counts, baseline non-inflammatory lesion counts, and the results of the same variable from previous visits. The average score of the MI copies will be used to calculate the summary statistics.

Finally for missing IGA, lesion counts and CADI in the PP population, data will be summarized at week 12 where the primary handling method for missing data will be the Last Observation Carried Forward (LOCF). For the PP population, number of subjects who were discontinued prematurely due to documented lack of efficacy, worsening condition, or a TEAE is expected to be small. For these subjects the efficacy data from their termination visit will be assigned to the nearest corresponding scheduled visit that has been missed, and carried forward to the subsequent visits for the analysis.

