- 3. If subject is not a Screen Failure and SAFFL = "N" and TR01SDT is missing then reason excluded from safety population is "No confirmed dose of study drug.".
- 4. If subject is not a Screen Failure and SAFFL = "N" and TR01SDT is not missing then reason excluded from safety population is "No post baseline safety data.".
- 5. If subject is not a Screen Failure and ITTFL = "N" then reason excluded from ITT population is "Not randomized and dispensed study drug.".
- 6. If subject is not a Screen Failure and PPROTFL = "Y" and ITTFL = "N" then reason excluded from PP population is "Not in ITT population.".
- 7. If subject is not a Screen Failure and PPROTFL = "Y" and ITTFL = "Y" then reason excluded from PP population is "Did not complete Week 12 evaluation without any major protocol violations."

Listing 16.2.4.1 Demographics and Baseline Characteristics

						Fitzpatrick Skin
Study						Type Classification
Populations 1	for				IGA Scale at	Scale at Baseline
Analyses	Age	Gender	Race	Ethnicity	Baseline [1]	[2]
None	XX	Male	White	Hispanic or Latino	0	I
Safety		Female	Black or African American Asian	Non-Hispanic or Non-Latino	1	II
ITT			American Indian or Alaska Native	Unknown	2	III
PP			Native Hawaiian or Other Pacific Islander		3	IV
			Other		4	V
						VI
	Populations : Analyses None Safety ITT	Populations for Analyses Age None xx Safety ITT	Populations for Analyses Age Gender None xx Male Safety Female ITT	Populations for Analyses Age Gender Race None xx Male White Safety Female Black or African American Asian ITT American Indian or Alaska Native PP Native Hawaiian or Other Pacific Islander	Populations for Analyses Age Gender Race Ethnicity None xx Male White Hispanic or Latino Safety Female Black or African American Asian Non-Hispanic or Non-Latino ITT American Indian or Alaska Native PP Native Hawaiian or Other Pacific Islander	Populations for AnalysesAgeGender GenderRaceEthnicityBaseline [1]NonexxMaleWhiteHispanic or Latino0SafetyFemaleBlack or African American AsianNon-Hispanic or Non-Latino1ITTAmerican Indian or Alaska NativeUnknown2PPNative Hawaiian or Other Pacific Islander3

Note: ITT = Intent-to-Treat. PP = Per-Protocol

Program: L-xxx .sas Programmer: xxx ddmmmyyyy

^{[1] 0 =} Clear; 1 = Almost Clear; 2 = Mild; 3 = Moderate; 4 = Severe

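### The per-protocol exception depends on leaving the study, not on stopping product, so a subject who stops product for a treatment-related AE by about Day 67 is in PP if they leave and, on the plain reading, out if they stay to Week 12; the PP flags in Listing 16.2.3 are also reversed

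*SAP*

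**What the plan says.** SAP 6.5.4 builds the PP population in two steps. First, "the PP population will include subjects in the ITT population who meet all of the following criteria": eligibility (criterion 1), no disqualifying prohibited medication (2), a Week 12 visit in its window (3), and 80% to 120% of expected applications across the whole evaluation period, with 168 printed as the expected number (4). It then adds that "Subjects who prematurely discontinued from the study due to documented lack of efficacy, worsening condition, or a treatment-related AE will be included" in PP. Protocol 11.2.3 has the same structure without the 168: "Subjects who prematurely discontinue from the study due to documented lack of efficacy, worsening condition, or a treatment-related AE will be included in the PP".

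The protocol treats stopping product as a different event from leaving. Section 7.7 item 3 says: "Subjects who experience an AE resulting in or requiring discontinuation of study product use should be encouraged to be followed in the study", and sets the end of that follow-up at resolution or stabilization of the AE. Section 8.5 also names withdrawal and stopping product as alternatives.

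SAP 8.3 says how leavers in PP contribute efficacy data: the termination-visit value goes to the nearest missed visit and is carried forward. It says that the number "discontinued prematurely due to documented lack of efficacy, worsening condition, or a TEAE is expected to be small". SAP 6.5.4 and protocol 11.4 refer to a treatment-related AE at that point, not to any TEAE.

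In SAP Listing 16.2.3, note 1c lists a subject as PP when PPROTFL is Y. Note 7 nevertheless reads "If subject is not a Screen Failure and PPROTFL = 'Y' and ITTFL = 'Y' then reason excluded from PP population is", followed by a reason for exclusion. Note 6 uses the same PPROTFL value with ITTFL = N. Footnote [3] describes PP as subjects who completed Week 12 without major violations and leaves out the exception.

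**The concern.** Two subjects can have the same AE, the same relatedness and the same last dose, and still differ in PP status only because one left and the other kept attending. The leaver enters PP with a carried-forward value, while the stayer's observed Week 12 data are dropped.

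The case is foreseeable. Protocol section 8 reports desquamation, dry skin, erythema and burning in 10% to 30% of subjects in acne trials of the comparator cream, so product stops for local reactions are plausible.

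At stake are the PP summaries of IGA success, lesion counts and CADI, which would depend partly on how well sites retain subjects who are off product. The listing error is a different matter: Listing 16.2.3 is the record of who was left out of PP and why, and as specified it would not show that.

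**Working it through.** **1. The plan's figure.** Inputs are two lotion applications per day or one cream application per day (SAP 4.1), over 84 days (Week 12 = Day 84).
- Lotion: 2 × 84 = 168, which reproduces the number in criterion 4.
- Cream: 1 × 84 = 84, which does not.

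**2. The 80% cut for a subject who stays.** Assume no missed doses before the stop.
- Lotion: 0.80 × 168 = 134.4, so 135 applications are needed. At two per day this is reached on Day 68. A stop on Day 67 gives 134/168 = 79.8% (fails); Day 68 gives 136/168 = 81.0% (passes).
- Cream, 84 expected: 0.80 × 84 = 67.2, so 68 applications are needed, again reached on Day 68. A stop on Day 67 gives 67/84 = 79.8%.
- Cream, printed 168: full use gives 84/168 = 50.0%, or 89/168 = 53.0% if the Week 12 visit falls on Day 89. Every cream completer then fails criterion 4, whether or not product was stopped early.

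Missed doses before the stop move the cut later.

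**3. Same subject, leaving or staying (lotion, treatment-related AE).**

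| Product stopped | Applied/expected | Leaves the study | Stays to Week 12 in window |
|---|---|---|---|
| Day 28 | 56/168 = 33.3% | in PP | out (criterion 4) |
| Day 56 | 112/168 = 66.7% | in PP | out (criterion 4) |
| Day 67 | 134/168 = 79.8% | in PP | out (criterion 4) |
| Day 75 | 150/168 = 89.3% | in PP | in PP if the other criteria are met |

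**4. The competing compliance reading.** Protocol 6.2.3 says that no application counts as missed after the last treatment date. If compliance were applied/(applied + missed), the Day 28 stayer would have 56/(56 + 0) = 100% and would pass. Criterion 4, however, divides by expected applications over the entire evaluation period, and protocol 11.5.1 names that period as Baseline to Week 12. The plain reading is therefore the one in step 3.

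**5. Listing 16.2.3.** Notes 3 to 5 give exclusion reasons for the Safety and ITT populations when the flag is N. Notes 6 and 7 do so for PP when the flag is Y.
- Note 6 (PPROTFL = Y, ITTFL = N) cannot occur, because PP is a subset of ITT.
- Note 7 (PPROTFL = Y, ITTFL = Y) is true of every PP member.
- A randomized subject with PPROTFL = N matches neither note.

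As written, PP members get an exclusion reason, and excluded subjects other than screen failures get none.

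**The case against.** Several stronger readings are tempting, and the documents do not support them.

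- A reader might infer that protocol 7.7 item 3 asks subjects to stay to Week 12. It asks for follow-up until the AE is resolved or stabilized. A subject who leaves after that may still fall under the exception, so the contrast needs someone who goes on to complete Week 12. Nothing prevents this, but no rate is given.
- A reader might take the exception to readmit leavers who were ineligible or took prohibited medication. The text does not say so. It can equally be read as relieving only what early departure makes impossible, namely criteria 3 and 4. This calls for clarification and is not a proven error.
- A reader might infer that SAP 8.3 widens PP to any TEAE. Membership is set in 6.5.4; 8.3 describes data handling, and its wording is merely loose. Footnote [3] likewise abbreviates the opening sentence of 6.5.4 and is not a rival definition.
- Protocol 6.2.3 could rescue the stayer (step 4). Criterion 4 as worded points the other way, but the two passages are not reconciled.

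The best point against is impact. The PP summaries are descriptive and secondary, the trial is not powered, SAP 8.3 expects few such leavers, and Listing 16.2.3 names ITT as the primary efficacy set. Take assumed counts in one arm of 36 completers with 11 successes plus 4 product-stoppers with none. PP success then runs from 11/40 = 27.5% if all four leave to 11/36 = 30.6% if all four stay, a shift of 3.1 points. The standard error of 11/40 is √(0.275 × 0.725/40) = 7.1 points. No between-arm distortion can be shown from the documents. All of this limits the weight of the point; it does not remove the asymmetry in the rule.

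**Conclusion.** The point holds in a limited form. In both documents the exception is tied to leaving the study. A stayer with the same reason and last dose has no exception and, on the plain reading of criterion 4, is excluded when product stops by about Day 67. This assumes full use before the stop and a denominator of 168 for lotion. It extends to cream only with a denominator of 84; with the printed 168, cream completers fail criterion 4 in any case.

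The number of subjects affected cannot be derived. The effect is confined to the descriptive PP efficacy summaries. A reader might infer that the primary comparison is compromised, but local tolerability and TEAEs are analyzed in the Safety population (SAP 3.2.1 and section 9).

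The reversed flag in Listing 16.2.3 needs no assumption: note 7 contradicts note 1c of the same listing. It is a separate programming error and does not add weight to the PP-rule argument.

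**What to change.** Before database lock:

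1. In Listing 16.2.3, change PPROTFL from Y to N in notes 6 and 7, and add the exception to footnote [3].
2. Reword the SAP 6.5.4 exception to cover subjects who permanently stop product for the listed reasons, whether or not they remain in the study. State that it waives criteria 3 and 4 only. Because protocol 11.2.3 has the same wording, record this as a departure from the protocol; both documents already allow additional PP criteria to be documented and signed before lock.
3. State one rule for the efficacy value that these subjects contribute. Without it, a leaver who stopped on Day 21 contributes an early carried-forward value, while a matching stayer contributes a Week 12 value taken 84 − 21 = 63 days after the stop. A rule anchored to the time of product stop could be applied to both.
4. Use the treatment-related wording in SAP 8.3.
5. Reconcile the criterion 4 denominator with protocol 6.2.3 and with the once-daily cream schedule.

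The cost is SAP wording, two flag corrections, one derivation and a recorded departure. For AEs, relatedness and whether product was continued are already recorded (protocol 8.2). For lack of efficacy or worsening condition, the listing shells show a reason only for leaving the study, so check that the eCRF records why product was stopped. The small downside is that PP keeps a few more low-exposure subjects.

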6.6. Baseline Definition

Baseline assessments are defined as the last non-missing result prior to administration of the first dose of study medication. If there are multiple assessments collected at the same scheduled time, the average of these

assessments will be used. If baseline is missing, then substitute the last screening value if available. If both baseline and screening is missing, then baseline is missing.

6.7. Derived and Transformed Data

6.7.1. Baseline Age

Subject's age in years will be calculated based on the date of the Baseline Visit date using the following formula:

Age (years) = FLOOR((INTCK('month', Date of Birth, Date of Baseline Visit) - (DAY(Date of Baseline Visit) < MIN(DAY(Date of Birth), DAY (INTNX ('month', Date of Baseline Visit, 1) - 1))) /12)⁷ where:

- FLOOR() is a SAS function that returns the largest integer that is less than or equal to the argument.
- INTCK() is a SAS function that returns the number of interval boundaries of a given kind that lie between two dates, times, or datetime values.
- DAY() is a SAS function that returns the day of the month from a SAS date value.
- INTNX() is a SAS function that increments a date, time, or datetime value by a given time interval, and returns a date, time, or datetime value.

6.7.2. Study Day

For this study:

- Day 1 is defined as the day of the first dose.
- For a visit date on or after the date of the first dose: Study Day = (date of interest date of first dose) + 1
- For a visit date before the date of the first dose: Study Day = (date of interest date of first dose)

6.7.3. Change from Baseline

Change from baseline is calculated as (post-baseline result – baseline result). Data will not be imputed for a specific post-baseline time point if the data was not recorded. Changes from baseline will be calculated based on the matched pairs of data points (subjects with data at both baseline and post-baseline).

Percent change from baseline is calculated as (change from baseline/baseline result * 100).

If either the baseline or the post-baseline result is missing, the change from baseline and/or percentage change from baseline will be set to missing.

6.7.4. Visit Windows

Visit windows for study DFD-03-CD-005 are displayed in Table 3.

Table 3: Visit Windows

Study Phase	Visit	Day	Visit Window
Screening	Visit 1 ¹	Screening	Day -60 to 0
Baseline	Visit 2 ¹	Baseline Day 1	Day 1
Treatment	Visit 3	Day 28 (Week 4)	Day 25 to 31
	Visit 4	Day 56 (Week 8)	Day 51 to 61
	Visit 5	Day 84 (Week 12)	Day 79 to 89

6.7.5. Multiple Assessments

If there are multiple assessments collected at the same visit, the average of these assessments will be summarized in tables. The worst result for a visit will be used when a table is created to present abnormalities. Listings will list all data by visit, date and time.

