3.2. Study Endpoints

3.2.1. Primary Endpoints

The primary safety endpoints are:

- Local Cutaneous Safety Evaluation Data (dryness, non-lesional erythema, peeling, stinging, burning, and itching). Reactions on the face were assessed separately from those on the chest/back/shoulders.
- Treatment-Emergent Adverse Events (TEAEs).

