8.1.1. Investigator's Global Assessment (IGA) of the Face

The IGA scale used in the study is a measure of static evaluation of qualitative overall acne severity. IGA is an ordinal scale with five severity grades (reported only in integers, e.g., 0 to 4). Each grade is defined by a distinct and clinically relevant morphologic description to minimize inter-observer variability (Table 5). The grades on the scale have been sufficiently defined to appropriately and unambiguously represent each severity grade on the scale. The investigator was required to perform IGA scoring at each visit. The IGA was always done prior to lesion counts.

Table 5: IGA Scale for Facial Acne Vulgaris

Grade	Description ¹
0	Clear skin with no inflammatory or non-inflammatory lesions
1	Almost clear; rare non-inflammatory lesions with no more than rare papules
2	Mild severity; some non-inflammatory lesions with no more than a few inflammatory lesions (papules/pustules only, no nodular lesions)
3	Moderate severity; up to many non-inflammatory lesions and may have some inflammatory lesions, but no more than one small nodular lesion
4	Severe; up to many non-inflammatory and inflammatory lesions, but no more than a few nodular lesions

¹ Areas other than the face and nose were not included in assessment.

Enrollment of subjects with mild acne (IGA Grade 2) at each site was restricted to no more than 20% of total enrollment at that site; management of this requirement was handled by the IWRS.

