9.2. Local Cutaneous Safety Evaluation

Non-lesional erythema, peeling, dryness, stinging, burning and itching scores will be summarized by treatment group and visit including sample size, frequency count and percentage for each visit. A similar summary will be provided excluding subjects with signs or symptoms present at Baseline.

Non-lesional erythema, peeling, dryness, stinging, burning and itching scores and their corresponding descriptions are listed in Table 7, Table 8, Table 9, Table 10, Table 11 and Table 12 respectively.

Table 7: Scoring of Non-Lesional Erythema

Severity	Score	Description
None	0	No erythema
Mild	1	Light pinkness present
Moderate	2	Definite redness, easily recognized
Severe	3	Intense redness

Table 8: Scoring of Peeling

Severity	Score	Description
None	0	No peeling
Mild	1	Barely perceptible shedding, noticeable only on light scratching or rubbing
Moderate	2	Obvious but not profuse shedding
Severe	3	Heavy scale production

Table 9: Scoring of Dryness

Severity	Score	Description
None	0	No dryness
Mild	1	Slight barely perceptible fine superficial scale
Moderate	2	Clearly perceptible fine scale giving skin a powdery appearance
Severe	3	Marked roughness, cracked skin with fissures

Table 10: Scoring of Stinging

Severity	Score	Description
None	0	No stinging
Mild	1	Slight sharp, tingling/stinging sensation; not really bothersome
Moderate	2	Definite sharp, tingling/stinging sensation; that
		is somewhat bothersome
Severe	3	Sharp, tingling/stinging sensation that has caused definite discomfort

Table 11: Scoring of Burning

Severity	Score	Description
None	0	No burning
Mild	1	Slight warm, burning sensation; not really bothersome
Moderate	2	Definite warm, burning sensation; that is somewhat bothersome
Severe	3	Hot, burning sensation that has caused definite discomfort

Table 12: Scoring of Itching

Severity	Score	Description
None	0	No itching
Mild	1	Slight itching; not really bothersome
Moderate	2	Definite itching that is somewhat bothersome, without loss of sleep
Severe	3	Intense itching that has caused pronounced discomfort; night rest interrupted and excoriation of the skin from scratching may be present

Overall cutaneous tolerance was graded at the Week 12 visit, or the last visit if earlier, using grades shown in Table 13 below.

Table 13: Overall Tolerance

Grade	Score	Description
Excellent	0	No signs of irritation during the study
Good	1	Slight signs of irritation during the study, which resolved by the end of the study

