9.6. Vital Signs

The following vital sign parameters will be summarized by visit and treatment group:

- Diastolic Blood Pressure (mm Hg)
- Systolic Blood Pressure (mm Hg)
- Pulse Rate (beats/min)

In general, if multiple results are reported within the given analysis visit window for the same parameter, the mean of the results will be used for summary statistics except for baseline, for which the last assessment will be used.

For all vital sign parameter, the continuous results will be summarized using descriptive statistics by visit and treatment group. The summary statistics are n, mean, median, SD, minimum and maximum. Boxplots for vital signs versus time by treatment for all time points will also be generated. Boxplots will display Baseline, Day 28, Day 56 and Day 84 assessments.

Changes from baseline will also be summarized by visit and treatment. The summary statistics are n, mean, median, SD, minimum and maximum. With respect to the mean change from baseline, the 95% confidence interval will also be computed. Boxplots for change from baseline versus time by treatment for all time points will also be generated. Boxplots will display Day 28, Day 56 and Day 84 assessments.

Potentially Clinically Significant (PCS) vital signs will be summarized by parameter. The summary will indicate the number of subjects with PCS-low or PCS-high values by visit and treatment group. The criteria for identifying PCS abnormalities for vital signs are summarized in Table 15.8,9

Table 15: Criteria for Potentially Clinical Significant Vital Sign Abnormalities

		Criteria	
Parameter	Age	PCS Low	PCS High
Pulse	5 to 14 years	\leq 50 bpm at any time post dose.	\geq 140 bpm at any time post dose.
(beats/min)	15 to 18 years	\leq 50 bpm at any time post dose.	\geq 120 bpm at any time post dose.
	18 and above	\leq 50 bpm at any time post dose.	\geq 110 bpm at any time post dose.
	Any	Any \geq 15 bpm decrease from baseline at any time post dose.	Any \geq 15 bpm increase from baseline at any time post dose.
Systolic Blood	7 to 12 years	≤ 117 mm HG at any time post dose.	≥ 130 mm Hg at any time post dose.
Pressure (mm Hg)	13 to 17 years	≤ 120 mm HG at any time post dose.	≥ 144 mm Hg at any time post dose.
	18 and above	≤ 90 mm HG at any time post dose.	≥ 150 mm Hg at any time post dose.
	Any	Any \geq 20 mm Hg decrease from baseline at any time post dose.	Any \geq 20 mm Hg increase from baseline at any time post dose.

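### SAP 6.7.5 and 6.6 average repeat assessments for every variable, a rule that does not fit the integer tolerability grades or the IGA (low severity, few if any subjects affected)

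*SAP*

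**What the plan says.** The general rule for repeats is in SAP 6.7.5: "If there are multiple assessments collected at the same visit, the average of these assessments will be summarized in tables". It is followed by one exception: "The worst result for a visit will be used when a table is created to present abnormalities". The section does not say which tables those are. It also has the listings show every value.

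For baseline, SAP 6.6 takes the last non-missing result before the first dose and then adds a rule for ties: "If there are multiple assessments collected at the same scheduled time, the average of these" assessments is used. SAP 9.6 has its own rule for vital signs when several results fall in one analysis window: "the mean of the results will be used for summary statistics except for baseline, for which the last assessment will be used".

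SAP 3.2.1 names as a primary safety endpoint: "Local Cutaneous Safety Evaluation Data (dryness, non-lesional erythema, peeling, stinging, burning, and itching"). Each sign is graded 0 (none), 1 (mild), 2 (moderate) or 3 (severe) in SAP Tables 7 to 12. Under SAP 9.2 the "scores will be summarized by treatment group and visit including sample size, frequency count and percentage for each visit". On the IGA, SAP 8.1.1 says: "IGA is an ordinal scale with five severity grades (reported only in integers, e.g., 0 to 4"). IGA success (SAP 8.3) requires a score of 0 or 1 and a drop of at least 2 grades from baseline. Neither 9.2 nor 8.3 has its own rule for repeats.

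**The concern.** A mean is a reasonable summary of two blood pressures. It is not a reasonable summary of two ordinal grades that will be counted by category. If a subject has two different grades for one sign at one visit, the stated rule gives either a value that belongs in no row of the frequency table, or a valid grade lower than the worst one recorded. A programmer then has to round, drop or recode the value, and the SAP does not say which.

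The IGA has the same problem, with the added point that a fractional value can change success status. At Baseline, a tolerability average of 0.5 also leaves open whether the sign was present, which decides who enters the second summary in 9.2, the one that leaves out subjects who already had signs or symptoms at Baseline.

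**Working it through.** The plan states no figure on this point, so there is nothing to reproduce. The check applies the written rule to every case it could meet.

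**Inputs.** Tolerability grades 0, 1, 2, 3 (SAP Tables 7 to 12). IGA grades 0 to 4 (SAP 8.1.1). Eligible baseline IGA 2 or 3 (Protocol 5.2, criterion 5). IGA success definition (SAP 8.3). Planned arms of 50, 50, 25 and 25 (SAP 4.4).

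**Tolerability.** Two unequal grades a and b have average (a + b)/2. There are 4 × 3/2 = 6 such pairs:

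| Grades | Average | Worst | Under averaging |
|---|---|---|---|
| 0, 1 | 0.5 | 1 | no category |
| 0, 2 | 1.0 | 2 | moderate shown as mild |
| 0, 3 | 1.5 | 3 | no category |
| 1, 2 | 1.5 | 2 | no category |
| 1, 3 | 2.0 | 3 | severe shown as moderate |
| 2, 3 | 2.5 | 3 | no category |

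Four of 6 have no category, 2 of 6 are valid but too mild, and none returns the worst grade. Of the 3 pairs that contain a severe grade, none stays severe. Taking the highest grade puts all 6 in a defined category and keeps all 3 severe grades.

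**IGA.** There are 5 × 4/2 = 10 unequal pairs, of which 6 have a non-integer average. Three examples under the literal success definition:

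- Baseline repeats of 2 and 3 average 2.5. With Week 12 IGA 1, the reduction is 2.5 − 1 = 1.5, which is below 2: failure.
- Baseline 3 with Week 12 IGA 1 gives 3 − 1 = 2: success.
- Baseline 3 with Week 12 repeats of 0 and 1 gives an average of 0.5. The reduction is 2.5, but 0.5 is neither 0 nor 1, so success is not met as written, although either single score would have met it.

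**Weight of one subject.** 1/50 = 2 percentage points in an active arm; 1/25 = 4 in a vehicle arm.

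**How often repeats could arise.** Protocol 7.6 schedules tolerability grading at Visits 2 to 5 with no repeat within a visit. The unscheduled-visit procedures (Protocol 7.10.6) list neither tolerability grading nor the IGA. If such grades are captured anyway, the tolerability table shell gives unscheduled assessments their own row. The documents give no expected number of repeats.

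**Baseline.** 6.6 and the notes under the vital-sign and physical-examination shells agree that baseline is the last value before the first dose. They part only over same-time repeats: 6.6 averages them for every variable, and 9.6 takes the last for vital signs.

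**The case against.** The best defence is that the worst-result sentence in 6.7.5 may already cover tolerability, since graded erythema or peeling could be called an abnormality. The section does not rule this out, so some ambiguity stands. But elsewhere the SAP attaches that word to vital signs (9.6) and physical examination (6.1), and 9.2 does not describe its tables that way. The plain reading leaves tolerability under averaging. The sentence does not help the IGA or 6.6.

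A second defence is that severe reactions stay visible. Worsening from Baseline is to be recorded as an adverse event (Protocol 7.6), adverse events are counted at maximum grade (SAP 9.3.4), discontinuation for irritation scores as poor on overall tolerance (SAP Table 13), and the listings show all values. This stands, and it limits the harm.

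Three stronger readings are tempting but not supported:

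- *That averaging reaches a withdrawal visit.* At withdrawal the investigator should, "if possible, perform all Week 12 visit-specific evaluations" (Protocol 7.7). A reader might infer that a Week 8 visit on Day 52 and a withdrawal on Day 60, both inside Day 51 to 61 of SAP Table 3, would be averaged. But 6.7.5 speaks of one visit, and these are two; window wording appears only in the vital-signs rule. Efficacy data from a termination visit go to the nearest scheduled visit that was missed (Protocol 11.4; SAP 8.3 for the PP population), and Week 8 was not missed. That the SAP does not place termination-visit tolerability grades is a separate gap.
- *That the more irritating arm is understated most.* This needs repeat grading prompted by reactions, and no procedure calls for it.
- *That the baseline definition conflicts throughout.* The conflict is confined to vital-sign repeats.

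**Conclusion.** The point holds as a wording defect of low severity. Wherever two unequal tolerability grades or IGA scores are recorded at one visit, or at one scheduled baseline time, the stated rule gives a value with no category or one milder than the worst seen. This rests on the plain reading that the tolerability tables are not tables of abnormalities. On the other reading the SAP still does not say which rule governs a primary endpoint.

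The number of subjects affected is unknown and is likely to be very small or zero, because no repeat grading within a visit is planned. The 2- and 4-point figures are the weight of a single subject at the planned arm sizes, not an estimate of bias, and no direction between arms can be claimed. The study is descriptive and was not powered for significance (SAP 4.3), so no test result is at stake. The vital-sign baseline inconsistency is real but narrow.

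**What to change.** Before database lock:

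- In SAP 6.6 and 6.7.5, limit averaging to continuous measures.
- In SAP 9.2, state that the highest grade recorded at the visit is tabulated for each tolerability sign and each location (face; chest, back and shoulders). This matches the maximum-grade convention already used for adverse events in 9.3.4.
- For the IGA, use the last assessment recorded at the visit. A rule based on closeness to the target day would not separate two assessments made at the same visit.
- Define baseline as the last pre-dose assessment for every variable, in line with 9.6 and the shell notes, and say that this rule takes precedence over the two above at Baseline.

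The cost is a few sentences of SAP text, with no new data and no change to the table layouts. The one downside is that, if repeats do occur, reported irritation may be slightly higher in all arms.
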